## 9.6 Adverse Event Reporting

The AE reporting period starts with randomization and continues through the Week 32 study visit. Patients in this study who experience a drug-related AE or SAE will be followed until the AE or SAE is resolved or stabilizes per the Investigator's judgment, even if this occurs after the final study visit. All AEs spontaneously reported by the patient and/or in response to an open question from study personnel or revealed by observation, physical examination, or other diagnostic procedures will be recorded and reported on the appropriate CRF. When

a unifying diagnosis has been made that accounts for several possible signs and/or symptoms, the unifying diagnosis should be selected as the AE term. For example, the combination of general malaise, mild fever, headache, and rhinitis should be described as “upper respiratory syndrome” if this diagnosis has been made, rather than reporting the individual symptoms as separate events.

If any laboratory test is newly abnormal during the treatment or safety follow-up period, it will be followed at the discretion of the Investigator. Abnormalities of laboratory tests which are, in the opinion of the Investigator, clinically significantly worse compared to baseline, or for which a medical intervention is initiated, should be reported as AEs on the AE CRF.

### **9.7 Reporting of Serious Adverse Events and Adverse Events of Special Interest**

The SAE reporting period is the same as the AE reporting period. All SAEs that occur during the reporting period and regardless of causality must be reported by the Investigator to [REDACTED] by completing the SAE Form in the EDC system. Any pertinent source documents should also be submitted as soon as they are available. Do not withhold submission of an SAE even if complete information about the event is not available at the time of the initial report. Follow-up information on the SAE should be sent promptly by the Investigator when any additional relevant information about the event becomes known to the Investigator, or as requested by [REDACTED] or Corvidia Therapeutics.

#### **SAE and Pregnancy Reporting Contact Information**

[REDACTED]  
Telephone: [REDACTED]  
Facsimile: [REDACTED]  
e-mail: [REDACTED]

Hypersensitivity reactions (see [Section 8.2](#)) occurring during the Study Drug injection and anaphylaxis occurring anytime during Weeks 1 – 21 of the study should be reported in the EDC as adverse or serious adverse events on the AE and SAE CRFs within 24 hours of the site’s awareness of the event. Please submit as much information as is available with the initial report.

Corvidia Therapeutics will immediately notify the Investigator about important safety or toxicology information as it becomes available. It is the responsibility of the Investigator to promptly notify the IRB/ IEC about new and relevant safety information regarding the Study Drug, including serious adverse drug reactions involving risk to human subjects, in

accordance with the applicable policies. An unexpected event is one that is not listed by nature or severity in the [Investigator's Brochure](#).

## **9.8      Pregnancy Reporting**

If a woman who is a study patient becomes pregnant or a woman suspects she is pregnant from a male study patient, the Investigator should be informed immediately. The Sponsor must, in turn, also be notified by the Investigator immediately by completing a Pregnancy Form and faxing or emailing it to [REDACTED] (see [Section 9.7](#)). The pregnancy must be followed up through delivery or other fetal outcome. For any abnormal fetal outcome, including congenital anomaly or birth defect, spontaneous or therapeutic abortion, still birth, pre-mature birth, or other outcome other than live normal birth, the Investigator should promptly report to the Sponsor the abnormal fetal outcome on an SAE form.

## **10 STUDY ASSESSMENTS**

### **10.1 Pharmacodynamic Assessments**

#### ***10.1.1 CKD symptoms, Fatigue, and Health-Related Quality of Life***

CKD symptoms, fatigue, and health-related quality of life will be assessed with the PROMIS Fatigue 13a short form and selected items from the PROMIS fatigue item bank ([Appendix B](#)), Optum SF-36 v2® Health Survey PCS, MCS, and domain scores ([Appendix C](#)), PROMIS interest in sexual activity item ([Appendix B](#)), the Corvidia ePRO ([Appendix D](#)), the patient global impression of severity (PGIS) and the patient global impression of change (PGIC) ([Appendix E](#)), and the EQ-5D-5L ([Appendix F](#)).

#### ***10.1.2 Laboratory Assessments***

Evaluation of hs-CRP and hemoglobin are direct measure of IL-6 function. Serum albumin is also closely negatively correlated with inflammation. Key hematologic and iron metabolism assessments include Chr, TSAT, TIBC, ferritin, serum iron, and hepcidin.

Biomarkers of inflammation and cardiovascular risk include serum SSA, fibrinogen, NT-proBNP and ST2, which were chosen based on the documented detrimental effects of IL-6, and beneficial effects of anti-IL-6 therapies, on inflammation and on cardiac structure and function.

Biomarkers for CKD will be evaluated including cystatin C, creatinine, and urine albumin-to-creatinine ratio (UACR).

### **10.2 Safety Assessments (other than Adverse Events)**

#### ***10.2.1 Vital Signs***

Vital signs include temperature, respiratory rate, heart rate, and blood pressure. Whenever possible, vital signs will be obtained after at least 5 minutes resting in the supine position or, when necessary, in a semi-recumbent position. Vital signs will be done prior to ECG recordings.

#### ***10.2.2 12-lead ECG***

At specified time points, standard 12-lead ECG will be recorded in the supine position (or with the patient as flat as possible) after vital signs assessments. The ECG will be locally read by the Investigator.

### ***10.2.3 Physical Examination***

Scheduled (limited) physical exams must include at a minimum an examination of the skin, oropharynx, lungs, heart, abdomen, extremities (including feet), and any areas suggested by symptoms, with particular attention to signs of infection.

### ***10.2.4 Clinical Laboratory Testing***

Details on the collection, processing, storage, and shipment of central lab samples are contained in the Laboratory Manual. Coagulation: INR (only for patients on warfarin) will be performed at the Local Laboratory.

## 11 STATISTICAL CONSIDERATIONS AND DATA ANALYSIS

The study design and objectives are described in [Sections 2.0](#) and [3.0](#), respectively. Details of all planned analyses are provided in the Statistical Analysis Plan (SAP).

### 11.1 Sample Size

The primary efficacy endpoint is percent change from baseline in hs-CRP (average of the hs-CRP value prior to randomization and Day 1) to Week 13 between each active group and placebo. Based on the observed treatment difference in percent change from baseline in hs-CRP of -60.74% between combined COR-001-01 active groups and placebo and the associated pooled SD of 16.893% in hs-CRP at Week 4 from the final analysis of study COR-001-SC1, a sample size of 54 per group yields more than 99% power with 2-sided alpha=0.05. Taking into consideration the dropout rate of 10% by the end of the study, a sample size of 60 per group is planned for this study

Approximately 240 patients (60 per group) will be randomized.

### 11.2 Randomization

Approximately 240 patients will be randomized 1:1:1:1 to Ziltivekimab Dose #1 (7.5 mg), Ziltivekimab Dose #2 (15 mg) or Ziltivekimab Dose #3 (30 mg) or Placebo as they became eligible to proceed with dosing on Day 1. Patient randomization will be stratified by baseline hemoglobin ( $\geq 11$  or  $< 11$  g/dL) and CKD stage (3, 4 or 5). Approximately 240 patients will be randomized 1:1:1:1 (60 per group) into the trial.

### 11.3 General Statistical Considerations and Definitions

#### 11.3.1 General Statistical Methods

All study-collected data will be summarized by treatment group for the appropriate analysis population, using descriptive statistics, graphs, and/or raw data listings. Descriptive statistics for continuous variables will include number of patients (n), mean, standard deviation (SD), median, quartiles (Q1 and Q3), minimum (min) and maximum (max) values. Analysis of categorical variables will include frequency and percentage.

#### 11.3.2 Analysis Populations

**Intent-to-Treat (ITT) analysis population:** all patients randomized.

The ITT analysis populations will be the primary population for the analyses of disposition and baseline data and efficacy endpoints.

**Per-Protocol analysis population:** all patients randomized who completed the study and did not incur a significant protocol violation

For the ITT analysis populations and per-protocol populations, treatment classification will be based on the randomized treatment.

**Pharmacokinetics (PK) analysis population:** all patients randomized and who received at least one dose of Test or Reference product and who had at least one post-dose PK blood sample

**Safety analysis population:** all patients randomized and who received at least one dose of Test or Reference product.

For the PK analysis population and safety population, treatment classification will be based on the treatment actually received.

### **11.3.3 Analysis Windows and Baseline**

If data are collected by visit, the data will be analyzed by visit based on the protocol-planned visits. If multiple records are collected for a visit, the latest record will be used for the summary for that visit.

The observational period for the study will start from informed consent and end with study completion (see [Section 4.4](#) for the definition of study completion). Any event occurring after the defined observational period, even if collected on the CRF, may not be included in the planned statistical analysis. However, all data, including that reported after the defined observational period, will be included in the patient data listings.

For evaluations that are collected at multiple occasions prior to initiation of Study Drug, the latest evaluation will be considered the "Baseline" evaluation for analysis, unless otherwise specified.

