#### **4.8 Study Completion**

Primary study completion is defined as the completion of the Week 24 visit, even if one or more interim visits or procedures was/were missed.

Completion of the Safety Follow-Up is defined by the completion of the Week 32 visit even if one or more interim visits or procedures was/were missed.

---

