## 5.6 Early Termination Visit

There are two possible types of Early Termination visits:

**Early Termination Visit 1 (ET-1):** Randomized patients terminating from the study prematurely prior to Study Week 24 should undergo an Early Termination Visit during which Week 24 procedures are performed.

**Early Termination Visit 2 (ET-2):** Randomized patients terminating from the study prematurely after Study Week 24 visit, but before Week 32 should undergo an early termination visit during which Week 32 procedures are performed.

Criteria for discontinuation of Study Drug can be found in [Section 4.3](#).

Patients may be withdrawn from the study for a number of reasons, including those outlined below:

- Patients withdrawing their consent for all study procedures. Patients must be given the option to continue to give consent for passive follow-up (i.e. by means of chart review) for adverse events through Study Week 21.
- Discontinuation of the study by the Sponsor.

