### **9.3 Adverse Events of Special Interest**

The following adverse events of special interest must be reported to the Sponsor within 24 hours of the Investigator's awareness, even if not meeting the definition of a serious adverse event:

- Serious infections.
- Severe injection-related reactions.
- Gastrointestinal perforations.
- Hypersensitivity reaction during study drug administration.
- Anaphylaxis occurring at any time, even if considered unrelated to the study drug. A CRF for the collection of the details of such reactions will be available in the EDC.
- Neutrophil  $<500/\text{mm}^3$  (severe), or neutrophil  $<1000/\text{mm}^3$  (severe) with evidence of concurrent infection. These events will be separately summarized by treatment group and dose.
- Thrombocytopenia (platelet count  $<50,000/\text{mm}^3$  (severe)) or platelet count  $<75,000/\text{mm}^3$  (moderate) with evidence of concurrent TIMI major bleeding. These events will be separately summarized by treatment group and dose.
- Malignancies
- Description of additional safety assessments by treatment group and dose: vital signs, ECG, clinical laboratory, and anti-drug antibodies (binding and neutralizing).

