#### **11.4.5       Safety Analysis**

##### **11.4.5.1    Adverse Events**

The adverse event verbatim descriptions (investigator terms from the CRF) will be classified into medical terminology using the Medical Dictionary for Regulatory Activities (MedDRA). Adverse events will be coded to primary System Organ Class (SOC) and preferred term (PT) using MedDRA, Version 21.0.

Treatment emergent adverse events (TEAEs) are defined as AEs that initiated or worsened on or after the date of first dose of study drug up to the end of safety-follow-up. For AEs occurring on the first dosing day, if the start time cannot be ascertained, the event will be counted as treatment-emergent.

Safety events of special interest (Section 9.3) will be summarized by dose group and treatment assignment.

An overview of AEs will be provided including counts and percentages of subjects with the following:

- Any TEAEs (overall and by maximum severity)
- Any study drug related TEAEs (overall and by maximum severity)
- Any TEAEs of special interest (overall and by maximum severity)
- Any serious AEs (SAEs)
- Any treatment-emergent serious AEs (TESAEs)
- Any TEAEs leading to discontinuation of study drug
- Any TEAEs leading to discontinuation of study
- Any AEs leading to death
- Any severe hematologic AEs (see [Section 11.4.5.7](#))
- Any severe non-hematologic AEs

The number and percentage of patients reporting TEAEs and SAEs for each preferred term will be tabulated by system-organ class, by system- organ class and severity, and by system-organ class and relationship to Study Drug. If more than one event occurred with the same preferred term for the same patient, the patient will be counted only once for that preferred term using the most severe or related occurrence for the summary by severity, or relationship to study drug, respectively.

Listings will be presented specifically for SAEs and TEAEs leading to discontinuation of study drug.

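### Three protocol sections (11.3.3, 5.6 and 9.7) conflict with, or leave unclear, the Week 32 end of safety collection and analysis

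*Protocol*

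**What the plan says.** The general rules agree on Week 32. Section 9.6 states: "The AE reporting period starts with randomization and continues through the Week 32 study visit". Section 9.7 adds: "The SAE reporting period is the same as the AE reporting period". Section 5.4 lists adverse events among the procedures at Weeks 28 and 32. Section 11.4.5.1 defines treatment-emergent events as those that "initiated or worsened on or after the date of first dose of study drug up to the end of safety-follow-up".

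Three sections sit badly with this.

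- **Section 11.3.3** runs the observational period from informed consent to study completion and says: "Any event occurring after the defined observational period, even if collected on the CRF, may not be included in the planned statistical analysis". It keeps such data in the patient listings. It refers to Section 4.4 for the meaning of study completion, but that section holds the anaphylaxis stopping rule. The definitions are in Section 4.8: "Primary study completion is defined as the completion of the Week 24 visit", followed by a separate sentence that ties completion of safety follow-up to the Week 32 visit.
- **Section 5.6** offers patients who withdraw consent for all procedures passive follow-up by chart review "for adverse events through Study Week 21". Section 4.6 makes the same offer with no end date.
- **Section 9.7** asks for reporting within 24 hours of "anaphylaxis occurring anytime during Weeks 1" to 21. Section 9.3 requires 24-hour reporting of "Anaphylaxis occurring at any time, even if considered unrelated to the study drug".

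**The concern.** An exclusion rule needs a fixed date. The one in 11.3.3 rests on a term whose cross-reference leads nowhere, and whose nearest match elsewhere, primary study completion, is Week 24. A programmer who follows that match would cut the tables eight weeks before the end point in the definition of treatment-emergent events.

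The Week 21 limit in 5.6 is of another kind. It governs collection, so what it loses cannot be recovered at analysis. The mismatch between 9.7 and 9.3 leaves sites unsure what must be reported within 24 hours after Week 21.

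The late weeks are not a formality. Section 3.5.2 bases follow-up to Week 32 on the clearance of the drug, and Section 4.6 gives the long pharmacodynamic effect as a reason to keep monitoring patients who stop treatment. The trial is meant to choose a dose for an outcome trial (Section 2) and has neither a Clinical Events Committee nor a Safety Assessment Committee (Sections 12.1, 12.2). The safety tables by dose should therefore have one clear window.

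**Working it through.** **1. Calendar.** The last day of Week w is 7 × w. Week 21 ends on Day 147, Week 24 on Day 168 and Week 32 on Day 224. These match the upper ends of the visit windows in Figure 5.

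**2. Time at issue, against Week 32.**

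| End point | Where it arises | Days before Day 224 | Share of 224 days |
|---|---|---|---|
| Week 24 | 11.3.3, only if study completion means primary completion in 4.8 | 224 − 168 = 56 | 56/224 = 25% |
| Week 21 | 5.6, patients who withdraw all consent | 224 − 147 = 77 | 77/224 = 34% |

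For a patient who withdraws all consent after dose 6, those 77 days (11 weeks) are essentially all the time after the last dose. For a patient who withdraws earlier the gap is smaller: with a last dose at Week 9, follow-up to Week 21 still covers 21 − 9 = 12 weeks after that dose.

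**3. Which reading of 11.3.3 is right?** For Week 24: the only definition in 4.8 that uses the phrase study completion is the primary one. For Week 32:

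- 3.4 makes safety follow-up one of the three study periods.
- 5.6 describes patients who leave the study between Week 24 and Week 32, so they are still in it after Week 24.
- 11.4.5.1 counts events to the end of safety follow-up.

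Week 32 is the better reading, but 11.3.3 does not state it.

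**4. Is drug still present in those weeks?** Section 3.5.4.1 gives a terminal half-life of 48 to 56 days in CKD patients. As a simple one-phase illustration, the fraction of the level after dose 6 that remains after t days is 2^(−t/half-life). Dose 6 falls on Days 141–147, the Week 24 visit on Days 162–168 and the Week 32 visit on Days 218–224.

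- **Week 24:** t runs from 162 − 147 = 15 to 168 − 141 = 27 days. Lowest 2^(−27/48) = 0.68, highest 2^(−15/56) = 0.83.
- **Week 32:** t runs from 218 − 147 = 71 to 224 − 141 = 83 days. Lowest 2^(−83/48) = 0.30, highest 2^(−71/56) = 0.42.

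That is roughly 70–80% at Week 24 and 30–40% at Week 32. The formula ignores absorption. The same section puts the mean time to peak after subcutaneous dosing at 8 to 15 days, so these figures show only that the weeks in question are exposed time.

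**The case against.** A reader might infer that the protocol has three competing adverse-event windows, and that event rates by arm depend on which one is followed. The text does not support this. No section ends an adverse-event window at Week 24. The general collection rules and the specific rule for the adverse-event tables all point to Week 32, and a specific rule would normally prevail over the generic sentence in 11.3.3. That sentence only permits exclusion and keeps the data in the listings.

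Nor does Week 21 apply to the trial at large. Patients who merely stop study drug stay for early-termination and safety follow-up procedures (4.3, 4.6), so the limit in 5.6 reaches only those who withdraw consent for all procedures. Anaphylaxis after Week 21 is still collected under 9.6 and is still an event of special interest under 9.3. A site that follows 9.3 also satisfies 9.7.

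All of this stands, and it narrows the point. It does not remove it. The cross-reference in 11.3.3 is wrong and its key term has two possible dates. Sections 5.6 and 4.6 give different instructions for the same patients. Section 9.7 is narrower than 9.3 for the same event. The last two are site instructions, which a statistical analysis plan cannot change.

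**Conclusion.** The point holds in limited form. Week 32 is the protocol's general end for safety collection and for counting treatment-emergent events. One section leaves the analysis cut-off undefined, one shortens collection for fully withdrawn patients, and one contradicts a 24-hour reporting duty.

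The size is conditional. The loss of 56 of 224 days (25%) from the tables arises only if study completion in 11.3.3 is read as primary completion. The loss of up to 77 days applies only to patients who withdraw all consent, agree to chart review, and would be followed under 5.6 rather than 4.6. It matters mainly for those who withdraw after dose 6. The protocol does not say how many that will be. For anaphylaxis, the conflict concerns rapid reporting after Week 21 and not whether the event is recorded. The residual-drug percentages are an illustration that rests on one-phase decay and the stated half-life.

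The effect on the comparison between arms is probably small. The correction is still worth making because a gap in collection cannot be repaired later.

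**What to change.** - **11.3.3:** replace the reference to Section 4.4 with Section 4.8. State that for safety data the observational period ends at completion of safety follow-up (Week 32 visit, or last contact if earlier), as 11.4.5.1 already implies. The exclusion sentence can then stay, since it would reach only later events.
- **5.6:** reconcile the Week 21 limit with 4.6 and 9.6 so that passive follow-up, where the patient agrees to it, runs to Week 32. State the same end in 4.6.
- **9.7:** reconcile the anaphylaxis reporting window with 9.3, so that sites have one rule.

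The cost is amendment wording, plus chart review to Week 32 for patients who withdraw from all procedures but consent to it. No visit, sample or analysis method changes.
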